Test the acceptability and feasibility of our brief motivational interview intervention to facilitate advance care planning (ACP) conversation on older adults with serious co-morbid illness being discharged from the emergency department (ED) and interview the participants to understand their perception and collect patient-reported outcomes data after leaving the ED.

Hypotheses

- a) $\geq 80\%$ of clinicians will find it acceptable to conduct this interview in the ED for appropriate patients;
- b) $\geq 80\%$ of patients will find the interview respectful to patient-oriented needs;
- c) $\geq 25\%$ of participants will have reported completing ACP conversation with their primary outpatient clinician at three month after leaving the ED.

Methodology

We will pilot test (Part I) the intervention to ED patients and interview 15 to 25 participants (depending on theme saturation) immediately following the intervention to explore how they perceived the intervention. After the intervention is administered, they will be asked to complete a Likert scale survey about acceptability. Additionally, we will collect pre-/post-intervention patient-centered outcome data (Part II) in-person at the time of intervention and via phone interview at three months after the ED visit for 100 patients.

III. SUBJECT SELECTION

Trained RAs will recruit the subjects using the inclusion and exclusion criteria (**Table 2**). We will use convenience sampling for this study. Each morning when a trained EM physician evaluates patients in the ED observation unit, the trained RAs will ask the physician to identify potential subjects based on inclusion and exclusion criteria.

| Inclusion | Exclusion |
|-------------------------------|--------------------------------------------------|
| ≥ 65 years of age | Acute physical or emotional distress |
| English-speaking | Determined by EM physician not to be appropriate |
| Capacity to consent | Clearly documented goals for medical care** |
| AND ≥ 1 Serious illness* | Already enrolled in this study |

*New York Heart Association stage 3 or 4 heart failure, oxygen-dependent chronic obstructive lung disease, chronic kidney disease on dialysis, and metastatic cancer. **MOLST, medical order for life sustaining treatment.

IV. SUBJECT ENROLLMENT

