We will collect pre-/post-intervention data to demonstrate the intervention's feasibility to improve patient-reported outcomes. We will measure patient-reported outcomes before (in-person) and three months after our intervention (over the phone). We will assess the proportion of participating older adults who self-reported having spoken to their primary outpatient physician and/or caregivers about their goals for end-of-life medical care following the intervention. We will use validated instruments to measure quality of life (QUAL-E),¹³ ACP engagement behavior (ACP Engagement Survey),¹⁴ patient empowerment (Patient Activation Measure – PAM™),¹⁵ and potential subjective distress caused by the intervention (a potentially traumatic event).¹⁶

Measurements

We will measure the proportion of patients who self-report having had the conversation with their outpatient physician. We will also use QUAL-E, a validated instrument to measure quality of life of patients with a range of diseases (cancer, congestive heart failure, chronic obstructive pulmonary disease, and end-stage renal disease).¹³ This instrument is particularly suited to measuring the quality of life of patients who may or may not have acknowledged the terminal nature of their disease, but who, nevertheless, are dealing with end-of-life issues. In addition, we will use the ACP Engagement Survey, a validated instrument developed based on Social and Behavior Change Theory, and it measures the full range of self-reported processes involved in ACP (e.g. changes in knowledge, contemplation, self-efficacy and readiness) as well as actions associated with ACP behavior.¹⁴ We will also use the PAM™, which is a validated instrument that measures the four stages of patient empowerment: (1) believing the patient role is important, (2) having the confidence and knowledge necessary to take action, (3) taking action to maintain and improve one's health, and (4) staying the course even under stress.¹⁵ To evaluate whether the ED intervention itself increases patient stress, we will also measure posttraumatic stress disorder symptoms using the Impact of Event Scale – Revised (IES-R).¹⁶ IES-R is a validated scale to assess subjective distress caused by traumatic events. The trained RAs will administer these instruments (see *Appendix*)

immediately before the intervention, and again by phone three months later. IES-R will only be used at three month.

Outcomes

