The primary outcome is the proportion of patients self-reporting having spoken to their primary outpatient physician regarding their preferences for end-of-life medical care three months after the ED intervention. The secondary outcomes are quality of life, ACP behavior change, PAM™, posttraumatic stress disorder symptoms, proportion of subjects with documented ACP conversation on medical records three months after the intervention. We will also track the rate of patients being lost-to-follow-up to aid in appropriate design of a future randomized clinical trial.

VI. BIostatistical Analysis

Variables to be collected

We will collect demographic information of our subjects from the electronic health records, including age, gender, prior ACP documentation, co-morbid medical conditions, and ED diagnosis. Both the administration of BMI intervention by a clinician and subsequent qualitative interview of the participants will be video-recorded to ensure fidelity of the intervention administration and accurate capturing of their inputs. We will also administer the validated survey instruments (ACP Engagement Survey, QUAL-E, PAM™, IES-R) and self-reported completion of ACP conversation three months after leaving the ED.

Study Endpoint

Part I – Acceptability Study

The study will conclude when 15 to 25 participants are enrolled and thematic saturation of the qualitative analysis is reached.

Part II – Feasibility Study

The study will conclude when 100 participants are enrolled and three month post intervention data is collected over the phone.

Statistical Methods

Part I Analysis

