We will employ a modified phenomenological approach to code for themes that illustrate patient's perception of the intervention. We selected phenomenology as our qualitative research strategy since it is particularly suited to explore how individuals experienced our intervention. The PI and the trained RA will immerse themselves in the text by reading and re-reading for content, quality, and patterns. During this time, the audit trail of notes will be kept by individual coders to be reviewed in a subsequent discussion group. After independent coding of 5 initial transcripts, the PI and the trained RA will determine the standard labeling for common patient perception themes; and these will be organized into a code book. We will iteratively re-organize the code book until the consensus is reached among the coders. If there are disagreements between the coders on a particular theme, we will employ a third coder to aid in judgment of the codes. The coders are

purposefully not blinded to the study questions because they need to decide what is pertinent to answer the study question at hand. The coders will use the code book to independently code the remaining transcripts. We will use Nvivo software to organize and manage our data. The study will conclude when new themes no longer emerge (thematic saturation is reached), based on agreement between the coders. If not, we will continue to recruit more subjects until thematic saturation is reached. The themes will be categorized and coders will decide with group consensus which quotes will be included as the representative quotes in the final manuscript. If there are disagreements, an additional researcher from the ED will be asked to review the quotes and themes.

Part II Analysis

We will calculate descriptive statistics of the patient-reported outcomes before and after the intervention. We will use one sample binomial exact test of proportions for categorical outcomes (e.g. proportion of patients reporting ACP conversations with their physicians), and Wilcoxon signed ranks test for ordinal outcomes (e.g. QUAL-E) at baseline and three months. We will use a p-value of 0.05 as the significance threshold.

Sample Size

Part I:

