We propose to enroll 10 to 25 subjects in Part I ~~this pilot study~~. In prior qualitative studies, this is the general number that a study like this takes to reach thematic saturation. We may enroll more than 25 subjects if we find that thematic saturation has not reached. We will submit an amendment to change the enrollment number should that occur.

Part II:

We propose to enroll 100 subjects in Part II. A recent meta-analysis of advance directive documentation studies demonstrated improvement in ACP completion rate ranging from 2 to 44% with an intervention.¹⁷ We assume that the baseline rate of ACP completion rate is <10% to be conservative. Base on prior similar studies, we assume our intervention will result in 25% increase in the rate of conversation above 10%. A sample of 100 subjects will afford us 97% power (two-tailed alpha of 0.05) to detect a difference of the conversation completion rates of 10% before the intervention versus 30% after the intervention. Power is also expected to be strong for the ACP behavioral change scale outcomes (our secondary outcome, similar preliminary data demonstrated a pre-to-post improvement of 0.5 SD).¹⁸ With a conservative assumption, we will have 85–98% power with our sample size.

VII. RISKS AND DISCOMFORTS

There is no risks and discomforts associated with procedures, drugs, devices, or radiation in this study.

Psychosocial Risks (Uncommon)

The participants will be introduced or re-initiated on the topic of ACP. Some patients with serious illness do not wish to discuss ACP because they feel uncomfortable with the topic. This potential discomfort, however, is a part of the

routine practice of EM. Many ED clinicians discuss ACP with patients routinely, and the study does not add additional discomfort that is different from the routine clinical practice. Further, PI is trained in serious illness communication and will be available to manage patients' anxiety and other emotions as needed.

VIII. POTENTIAL BENEFITS

Potential Benefits to Participating Individuals

It is our hope that the proposed intervention will empower patients to engage in ACP discussions with their primary outpatient clinician $\geq 25\%$ of the time three months after the ED visit. Further, this intervention may also improve other patient-reported outcomes without causing significant harm.

Potential Benefits to Society

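### Does the mention of caregivers in the Part II overview leave the primary outcome undefined?

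*Protocol*

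**What the plan says.** The protocol describes the Part II conversation outcome in several places.

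- Section V, Part II, opening paragraph: the proportion of participants who "self-reported having spoken to their primary outpatient physician and/or caregivers about their goals for end-of-life medical care following the intervention".
- Section V, Part II, Measurements: "We will measure the proportion of patients who self-report having had the conversation with their outpatient physician".
- Section V, Part II, Outcomes: the primary outcome is the "proportion of patients self-reporting having spoken to their primary outpatient physician regarding their preferences for end-of-life medical care", assessed three months after the intervention.
- Section II, Hypothesis (c): at least 25% of participants will have "reported completing ACP conversation with their primary outpatient clinician at three month after leaving the ED".
- Section VI, Variables to be collected: "self-reported completion of ACP conversation three months after leaving the ED", with no conversation partner named.
- Section VI, Part II Analysis: the example for the one-sample exact binomial test is the "proportion of patients reporting ACP conversations with their physicians".
- Section VI, Sample Size, Part II: 97% power with 100 subjects for "conversation completion rates of 10% before the intervention versus 30% after the intervention", again with no partner named.
- Section VIII: the hope is that patients will "engage in ACP discussions with their primary outpatient clinician" at least 25% of the time.

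**The concern.** The opening paragraph and the Outcomes paragraph define different events. A patient who discussed end-of-life wishes only with a caregiver is a success under the first and a failure under the second. This affects the primary outcome of Part II, and caregiver conversations appear nowhere among the listed secondary outcomes, so the sentence does not describe a declared separate endpoint. The list of variables, where one would look for the data item, does not say with whom the conversation is held, and Table 3 has no conversation item.

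The stake would be the wording of the three-month phone question. If it were one combined item, the physician-only rate could not be recovered afterwards. The study has one arm and a 25% target for clinician conversations, so no comparison group would carry the same over-count. The observed rate is also meant to inform a later randomized trial.

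**Working it through.** **Step 1. Set the passages side by side.**

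| Place in protocol | Who counts |
|---|---|
| Section II, Hypothesis (c) | clinician only |
| Section V, Part II, opening paragraph | physician, caregiver or both |
| Section V, Part II, Measurements | physician only |
| Section V, Part II, Outcomes (primary) | physician only |
| Section VI, Variables to be collected | not named |
| Section VI, Part II Analysis | physician only |
| Section VI, Sample Size, Part II | not named |
| Section VIII | clinician only |

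Six places name a partner. Five of them name only the physician or clinician, and these include the measurement statement, the formal primary outcome and the analysis example. One introductory sentence differs.

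**Step 2. Read the two silent places in context.** The entry in Variables to be collected is a shorthand item in a list, and it comes after the primary outcome has been defined. The sample-size paragraph powers a conversation rate and then turns to the behaviour-change scale, which it labels as secondary. The first quantity is therefore the primary outcome already defined. Table 3 lists instruments only and also omits the PAM, so it is not a complete list of data items.

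**Step 3. Does the planning figure depend on the wording?** Inputs from Sample Size, Part II: N = 100, 10% against 30%, two-sided alpha 0.05, stated power 97%.

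- Two proportions, unpooled: standard error = √(0.1×0.9/100 + 0.3×0.7/100) = √0.003 = 0.0548. Power = Φ(0.20/0.0548 − 1.96) = 95.5%, within 2 points of the stated figure.
- Paired McNemar, normal approximation, assuming 5% move from yes to no: 96.5%.
- Planned one-sample exact test against 10%, which rejects upwards from 17 of 100: 99.9%.

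Each calculation uses only the two rates, N and alpha, so aligning the overview sentence would leave it unchanged.

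**Step 4. Size of the effect if the item were combined.** The physician and caregiver-only rates below are assumptions, and all 100 patients are taken to answer.

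Caregiver-only talks needed to lift the count to 25 of 100:

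- 15 spoke to a physician: 25 − 15 = 10, and 10/85 = 11.8% of the rest
- 20 spoke to a physician: 25 − 20 = 5, and 5/80 = 6.3%
- 24 spoke to a physician: 25 − 24 = 1, and 1/76 = 1.3%

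Chance of at least 25, from P(X ≥ 25) = Σ C(100,k) pᵏ(1−p)¹⁰⁰⁻ᵏ for k = 25 to 100, with a true physician rate of 20%:

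| Caregiver-only | Counted rate | P(X ≥ 25) |
|---|---|---|
| 0% | 20% | 13.1% |
| 5% | 25% | 53.8% |
| 10% | 30% | 88.6% |

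For the exact test against 10%, with an assumed physician rate of 15%, the chance of 17 or more is 33%. A further 5% caregiver-only brings the counted rate to 20% and that chance to 81%.

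These figures show that a wider event occurs more often. They are not evidence that this study would count the wider event.

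**The case for a change.** The best case for a change is that the risk runs one way. A separate physician item loses nothing, whereas a combined item cannot be split after the calls are made. The ambiguity concerns the primary outcome, Step 4 shows that modest caregiver-only rates could move the result, and the correction would cost a few words.

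Part of this stands. The mismatch is real, the variable list could name the partner, and a combined question would do damage. But the damage requires whoever writes the question to follow one introductory sentence against the Measurements paragraph directly below it and against the formal outcome. No such question is in the text at hand. The instruments are said to be in an appendix that is not shown, so the missing question wording cannot be held against the plan. The overview phrase could equally describe two separately recorded items. Nor is 25% named as the null value of the planned test; it is the target in Hypothesis (c), so crossing 25 of 100 is only an illustration.

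**Conclusion.** No change to the plan is called for. The caregiver wording is a clerical slip in one overview sentence, and the unnamed partner in the variable list is a gap that the formal primary outcome fills. Following the Outcomes, Measurements and Part II Analysis text gives a physician-only rate. Aligning the stray sentence would alter neither the endpoint, the 100 subjects, the test nor the stated power.

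The shift from 13% to 54% or 89% would arise only under a combined phone question and the assumed 20% physician rate with 5% or 10% caregiver-only talks; the protocol establishes none of these. The conclusion rests on the ordinary convention that a formally stated primary outcome governs an introductory description, and on the three-month question following that outcome, as the Measurements paragraph says it will.

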There are two subject types in this study – ED clinicians and ED patients. ED clinicians (attending physicians and physician assistants) will be recruited to train in and administer the proposed intervention on ED patients. After the intervention is administered, they will be asked to complete a Likert scale survey about acceptability. Clinicians will be asked to participate voluntarily. The PI will make an announcement at the faculty / physician assistant meetings and hand out the study information sheet. ED patients will be recruited to be interviewed after the intervention to learn their perception of the intervention. Upon identification of the

potential subject, the trained RAs will approach the potential subject to explain the study and ask about their willingness to participate. Once the eligible subject agrees to participate, the PI will consent the patient to enroll. After the trained RAs explain the study, the subjects will have time to think about the enrollment until the PI physically arrives in the ED. The PI will review all study elements again with the subjects to ensure understanding of the study. Upon enrollment, the trained physician responsible for the care of the patient will administer the intervention. When a trained physician is not on duty in the ED observation unit, the PI will administer the intervention.

There will be no other methods of recruiting for this study. Since this is a single-armed, pre-/post-intervention assessment study, there will be no treatment assignment or randomization.

V. STUDY PROCEDURES

There will be two distinct parts of the study: acceptability study (Part I) using qualitative interviews to explore the patient’s perception of the intervention and quantitative assessment of clinician’s acceptability rating, and feasibility study to measure patient-reported outcomes (Part II) after leaving the ED for future randomized clinical trial. The timing of proposed data collection is shown on Table 3.

| Table 3 Timing of Proposed Data Collection and Instruments | | | | |
|------------------------------------------------------------|------------|--------------------------------------------------------|-----------------------|--------------------------------------------------------|
| Study Part | Subjects | Pre-Intervention | Post-Intervention | Three Month Follow-up |
| Part 1 | Clinicians | | Acceptability Survey | |
| | Patients | | Qualitative Interview | |

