| Part 2 | Patients | ACP Engagement Survey QUAL-E Survey IES-R Survey | | ACP Engagement Survey QUAL-E Survey IES-R Survey |

Part I: Acceptability Study

We will conduct in-depth, semi-structured interviews to understand patient’s perception of the intervention after its administration by a trained ED clinician. We anticipate to interview 15 to 25 patients, until thematic saturation of their perception is reached. Further, we will assess clinician acceptability by administering a Likert scale survey.

Measurements

Patient Perception Assessment: The PI and the trained RA will conduct the semi-structured interviews. The following domains will be explored: beliefs about formulating and communicating goals of care, experience of the ED intervention, and attitude towards further patient education about how to formulate goals of

care. Both the administration of BMI intervention by a clinician and subsequent qualitative interview of the participants will be video-recorded to ensure fidelity of the intervention administration and accurate capturing of their inputs.

Clinician Acceptability Assessment: Immediately after the clinician completes the encounter, we will ask to fill out an in-person survey to rate acceptability (Likert scale, 1 – not acceptable, 2 – somewhat unacceptable, 3 – neutral, 4 – somewhat acceptable, and 5 – acceptable).

Outcome Our primary outcome for the patient perception assessment of the study is to identify a recurring theme that illustrates the patient perception of the intervention. Our primary outcome for the physician assessment of the study is the proportion of administering clinicians who found the rating to be somewhat acceptable (4) or acceptable (5). Secondary outcomes are the time to administer the intervention and how often the 4 intervention components are appropriately completed.

Part II: Feasibility Study

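### The IES-R objective asks whether the ED intervention itself increases stress, which a single-arm study with one three-month score cannot estimate; it should be restated as descriptive

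*Protocol*

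**What the plan says.** - **Purpose.** Section V, Part II, Measurements: "To evaluate whether the ED intervention itself increases patient stress, we will also measure posttraumatic stress disorder symptoms". The opening of Part II treats the intervention as the potentially traumatic event to which the distress relates.
- **Timing in the text.** The same Measurements paragraph first says that the instruments are given "immediately before the intervention, and again by phone three months later", then makes an exception: "IES-R will only be used at three month".
- **Timing in Table 3.** The Part 2 row shows "ACP Engagement Survey QUAL-E Survey IES-R Survey" under Pre-Intervention and again under Three Month Follow-up.
- **Design.** Section IV: "Since this is a single-armed, pre-/post-intervention assessment study, there will be no treatment assignment or randomization".
- **Analysis.** Section VI, Part II Analysis, plans descriptive statistics before and after the intervention, an exact binomial test for categorical outcomes, and a Wilcoxon signed ranks test for ordinal outcomes at baseline and three months. It gives no threshold, reference value or margin for the IES-R.
- **Status and follow-up.** Section V, Part II, Outcomes, lists posttraumatic stress symptoms among the secondary outcomes and adds: "We will also track the rate of patients being lost-to-follow-up to aid in appropriate design of a future randomized clinical trial". No loss rate is assumed, and the 100 patients are not inflated for loss.
- **Harm language elsewhere.** Section VIII hopes that "this intervention may also improve other patient-reported outcomes without causing significant harm".

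**The concern.** The objective makes two claims that the design cannot meet. An increase needs a reference level, and attribution to the intervention needs a comparison with patients who did not receive it. Neither exists under the text of Section V.

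Between the conversation and the phone call, patients live through the rest of the ED episode and three months of advanced heart failure, oxygen-dependent lung disease, dialysis or metastatic cancer. Any of these can raise a distress score, including one nominally tied to the conversation. The score also exists only for patients who can be reached and are able to answer.

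At stake is what the pilot may say about harm. Its stated use is to inform a randomized trial. A low score reported against the present objective could be taken as showing that the intervention adds no stress, and a high score as showing that it does. The design supports neither statement.

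**Working it through.** The protocol gives no effect size, power or margin for the IES-R, so there is no figure to reproduce. The check sets the objective against what the data can yield, then shows what a descriptive estimate would be worth.

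**1. What the objective needs.** Let p1 be the proportion with high distress at three months after the intervention, and p0 the proportion the same patients would show without it. The objective concerns p1 − p0. A single arm with one score yields p1 only, and only for those assessed. Suppose p1 = 10% (assumed):

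| Unobserved p0 | Implied increase, p1 − p0 |
|---|---|
| 0% | 10 points |
| 5% | 5 points |
| 10% | 0 points |
| 15% | −5 points |

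Every row fits the same data. A small p1 does cap the increase in that proportion among those assessed, but it does not show that the increase is zero and says nothing about those not assessed.

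**2. Whether the named test applies.** Signed ranks requires a pair of scores for each patient. With IES-R taken once there is no pair. The descriptive statistics that Section VI also plans remain possible.

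**3. Whether the Table 3 baseline would help.** If Table 3 prevailed, the change from baseline would equal the intervention effect plus the change due to illness course and the ED visit. One equation with two unknowns does not identify the effect. A score about the conversation also has no clear meaning before the conversation has taken place.

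**4. Precision if all 100 are assessed.** Exact (Clopper-Pearson) 95% interval for 10/100: 4.9% to 17.6%. With no high scores, the upper limit is 1 − 0.025^(1/100) = 3.6%. If 70 were assessed (assumed), it is 1 − 0.025^(1/70) = 5.1%.

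**5. Effect of incomplete assessment.** The protocol gives no loss rate, so a range is shown. Assume that 10% of those reached score high. The bounds for all 100 count the unreached as none high, then as all high:

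| Reached | High among reached | Lower bound | Upper bound |
|---|---|---|---|
| 90 | 9 | 9/100 = 9% | (9+10)/100 = 19% |
| 80 | 8 | 8/100 = 8% | (8+20)/100 = 28% |
| 60 | 6 | 6/100 = 6% | (6+40)/100 = 46% |

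**6. Direction of bias.** Let q be the true rate, a the share of distressed patients reached and b the share of others reached. The observed rate is q·a / (q·a + (1−q)·b). With q = 20% (all values assumed):

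- a = 80%, b = 80%: 0.16/0.80 = 20.0%
- a = 60%, b = 80%: 0.12/0.76 = 15.8%
- a = 40%, b = 80%: 0.08/0.72 = 11.1%
- a = 80%, b = 60%: 0.16/0.64 = 25.0%

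The bias can run either way, and the documents give no data to say which.

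**The case against.** The best defence is that the IES-R is tied to an event. The protocol names the intervention as that event, so a post-only score is a coherent choice and the lack of a baseline is no defect in itself. The pilot states openly that it is uncontrolled and points to a later randomized trial. Distress is one of several secondary outcomes. It is also not the only source of evidence on harm: Part I interviews cover patients' experience of the intervention, and Section IX has the investigator watching for unexpected emotional distress.

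Most of this stands. It supports describing the distress that patients connect with the conversation. It does not support the words about an increase caused by the intervention itself, because a patient's own attribution is not a comparison. The other sources are uncontrolled as well.

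Three stronger readings are tempting, and the documents do not support them:

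- *The protocol plans to conclude that there is no harm.* It states no rule, threshold or margin for doing so. The sentence in Section VIII is worded as a possibility in a benefits section and does not mention the IES-R.
- *Death, illness and refusal will be merged into one loss rate.* Section V says only "We will also track the rate of patients being lost-to-follow-up". It does not say that reasons will be pooled, and reason codes and score cut-offs may sit in an SAP or case report form that is not shown.
- *Phone follow-up will understate distress.* The direction is unknown, as step 6 of the working shows.

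**Conclusion.** The objective is wrong as written. With one arm and one score, the size of any increase, and the part of it due to the intervention, cannot be estimated at any sample size. This follows from the text of Sections IV and V and needs no numerical assumption. Reconciling Table 3 in favour of a baseline would remove the single-score problem but not the confounding.

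The study can give a description of distress among patients assessed, with the precision and missing-data ranges shown in the working. Those ranges rest on an assumed 10% high-score rate and assumed numbers reached, and are illustrations only. A favourable result could not by itself support absence of harm.

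The consequence is limited. The primary outcome is untouched, and false reassurance is a risk of how the result might be read.

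**What to change.** - **Section V, Part II, Measurements.** Replace the stated purpose with a descriptive one: to describe, at three months, distress relating to the ED conversation as the index event, as Part II already implies.
- **Table 3 and text.** Make the two agree on when the IES-R is given. If a pre-intervention administration is kept, say which event the patient is asked about, and do not present the change as an intervention effect.
- **Section VI, Part II Analysis.** State that the IES-R is summarised by its score distribution with a 95% confidence interval among patients assessed, next to the number assessed out of all who received the intervention. If it is measured once, exclude it from the signed-ranks test.
- **Interpretation.** Add a sentence that the result shows neither an increase nor an effect attributable to the intervention, cannot by itself support absence of harm, and leaves attribution to the future randomized trial.

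Tabulating why patients were not assessed would help in planning that trial, but other study documents may already provide for it.

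The cost is a few changes of wording, with no new visits or instruments. The downside is a more modest statement about safety.
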